In our preliminary study (unpublished) with limited sample size, we compared two different bone marrow samples (CD138 selected DNA extract vs. formalin-fixed paraffin embedded (FFPE) bone marrow clot section) from same patients (from Moffitt Cancer Center) and demonstrated that high-throughput sequencing technology by Adaptive Biotechnologies can identify the index myeloma clones (data not shown). We hypothesize that high-throughput sequencing technology using PCR on CDR3 sequences will identify minimal residual disease in myeloma patients after autologous HCT followed by panobinostat maintenance and bone marrow samples will be obtained prospectively to analyze this technology.

3 Study rationale/purpose

Optimal maintenance therapy after autologous HCT in multiple myeloma has not been defined. Based on preclinical and clinical data demonstrating anti-myeloma activity of panobinostat, we propose an open-label, trial to determine the safety and tolerability of 2 dosing schedules of panobinostat maintenance therapy in patients with multiple myeloma who underwent autologous HCT. As noted in prior maintenance therapy in myeloma, the dose of maintenance single agent is usually started at a lower dose (such as 10 mg starting dose for lenalidomide maintenance compared to 25 mg full dose in relapsed/refractory disease treatment) due primarily to (1) lower disease burden after autologous HCT and (2) limited tolerability and susceptibility to cytopenias immediately after autologous HCT. Panobinostat maintenance therapy will be initiated between 90 days and 180 days after autologous HCT at a starting dose of (a) 20 mg PO three times a week, every other week, every 4 weeks (Cohort A), or (b) 10 mg po daily x 7 days, every other week, every 4 weeks (Cohort B). Maintenance therapy will be prescribed for a maximum for 12 cycles (4 weeks x 12 cycles = 48 weeks) for both cohorts. The dose delivered to each cohort would be 60 mg per week for Cohort A and 70 mg per week for Cohort B. Long-term tolerability of each dose schedule of panobinostat

maintenance therapy after autologous HCT is unknown and the study intends to evaluate the safety and tolerability in multiple myeloma patients.

4 Study objectives

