7.1 Investigational therapy

[figure not shown]
Screening consents will be signed prior to autologous HCT to access pre-HCT stem cell graft, bone marrow and peripheral blood samples for the correlative studies. Patients will be enrolled after autologous HCT. Patients will be initiated on panobinostat maintenance therapy between day +90 and +180 after autologous HCT. Patients who develop disease progression before day +90 after autologous HCT will be ineligible for the study.

Panobinostat (also known as LBH589) will be provided by Novartis. Oral panobinostat will be supplied as 5-mg, 10-mg, 15-mg or 20-mg pink/opaque-colored, hard gelatin capsules.

Medication labels will comply with US legal requirements and be printed in English. They will supply no information about the patient. The storage conditions for study drug will be described on the medication label.

During the study, panobinostat will be administered orally as either (1) once daily dose of 20 mg (1 x 20-mg capsule) three times per week, every other week, of a 28-day schedule (Cohort A), or (2) once daily dose of 10 mg (1 x 10-mg capsule) daily x 7 days, every other week, of a 28-day schedule (Cohort B). Both cohorts will receive a maximum of 12 cycles of maintenance therapy (Figure 7-1).

Figure 7-1. Panobinostat maintenance schedule

Patients should be instructed to take their once-a-day oral dose of panobinostat at the same time each morning. Each dose of panobinostat should be taken with an 8 oz / 240 ml glass of water. Patients should be instructed to swallow the capsules whole and not chew them. Patients must avoid grapefruit or grapefruit juice and seville (sour) oranges during the entire study.

If a subject experiences toxicity, the dose of panobinostat will be reduced to one level lower (Table 7-1) and maintained at this level for all subsequent cycles unless further toxicities occur. Panobinostat dose modifications will be made according to the toxicity grading. Once a subject's dose of panobinostat is reduced, then that dose will be the maximal dose administered.

On the days of ECG monitoring, drug administration should be supervised by study center personnel and administration time should be recorded.

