7.1.1 Cardiac precautions

All patients must have an assessment of serum potassium, magnesium, and calcium (total corrected for albumin, or ionized calcium) \leq 72 hours prior to the administration of oral panobinostat on day 1 of cycle 1 and the results must all be \geq LLN before the first dose of panobinostat is administered. Throughout the study serum biochemistry values including serum potassium, calcium, phosphorous and magnesium will be monitored closely. On any day and time in which serum potassium, calcium, phosphorous and magnesium are assessed, if the value is $<$ LLN, then the patient's potassium, calcium, phosphorous or magnesium should be immediately supplemented following the availability of that laboratory result, in order to minimize the time patients have low values. Patients must then undergo a repeat chemistry tests for repleted electrolytes (potassium, calcium, phosphorous or magnesium) to demonstrate values \geq LLN. These values must be \geq LLN before the patient is re-dosed with oral panobinostat.

Patients must be instructed to not take panobinostat if their most recent biochemistry values demonstrates potassium, calcium, phosphorous or magnesium $<$ LLN. At a minimum, potassium, magnesium, phosphorous and calcium will be checked according to the protocol. More frequent testing should be done if clinically indicated, e.g. patient has had prior low values, patient is taking medications (e.g., diuretics) that can result in lowering of their potassium, magnesium, phosphorous or calcium levels.

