7.3 Treatment cycle and duration

One treatment cycle consists of oral panobinostat either (1) 20 mg PO three times per week, every other week, of a 28-day schedule, or (2) 10 mg PO daily x 7 days, every other week, of a 28-day schedule. Patients may continue treatment with oral panobinostat until they experience unacceptable toxicity that precludes further treatment, disease progression, and/or at the discretion of the investigator. The planned treatment is for a total of 12 cycles (48 weeks).

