7.4.1 Dose reduction for panobinostat

This is an open-label trial to determine the safety and tolerability of single agent panobinostat (2 dosing schedules) as maintenance therapy after autologous HCT in patients with multiple myeloma. Patients will receive either 20 mg PO TIW, every other week, every 28-days (Cohort A) or 10 mg po daily x 7 days, every other week, every 4 weeks (Cohort B). If no grade 3 or 4 toxicities occur after completing a 28-day cycle of panobinostat maintenance therapy, and all non-hematologic toxicities improved to grade 1 or better, then the next cycle of panobinostat will be initiated as long as the minimal hematologic parameters are met (ANC $\geq 1 \times 10^9/L$; hemoglobin ≥ 8 g/dl; platelets $50 \times 10^9/L$) prior to each cycle. If a subject experiences toxicity, the dose of panobinostat will be reduced to one level lower (Table 7-1) and maintained at this level for all subsequent cycles unless further toxicities occur. Panobinostat dose modifications will be made according to the toxicity grading. Once a subject's dose of panobinostat is reduced, then that dose will be the maximal dose administered. The provisional dose levels of panobinostat (LBH589) to be investigated in this study are described in Table 7-1.

Table 7-1 Provisional dose reduction for panobinostat (LBH589)

Dose level#	Panobinostat oral dose	
	Cohort A (TIW, every other week, every 4 weeks)	Cohort B (Daily x 7 days, every other week, every 4 weeks)
1 (starting dose level)	20 mg	10 mg
-1	15 mg	10 mg on days 1, 3, 5, and 7

7.4.2 Dose modifications for study drug-related toxicity (see section 7.4.3 for dose modifications for prolonged QTc):

The criteria for dose modifications for study drug-related toxicity are detailed in [Table 7-2](#).

Table 7-2 Criteria for dosing delays, dose-reductions, and re-initiation of treatment due to study drug-related toxicity (excluding QT prolongation)

Worst Toxicity CTCAE Grade* unless otherwise specified (Value)	Dose Modification Guidelines At any time during a cycle of therapy (including intended day of dosing)	
HEMATOLOGICAL TOXICITIES		
Thrombocytopenia	Grade 3 (<50 and $\geq 25 \times 10^9/L$) with bleeding and Grade 4 (< $25 \times 10^9/L$)	Temporarily discontinue panobinostat dosing until resolved to \leq grade 2, or baseline, then, restart panobinostat at reduced level as per Table 7-1

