7.4.3 Dose modifications for prolonged QTc

All cardiac events should be treated as per the local standard of care and referred to a cardiologist if clinically indicated. The localized readings of ECGs will use the Fridericia correction for QTc interval assessment: QTcF. Any final decisions concerning dose modifications or permanently discontinuing the patient from study drug due to QTcF prolongation will be based on the Investigator's clinical assessment. Any plan to deviate from these guidelines must be previously discussed and agreed upon with Novartis.

Patients must have QTcF < 470 msec to be eligible for the trial. If QTcF is \geq 470 msec or above 60 msec from baseline on a screening or pre-dose ECG, correct any electrolyte abnormalities (hypokalemia, hypomagnesemia, hypocalcemia), and conduct triplicate ECGs (5 minutes apart) and calculate average QTcF. If the average QTcF from the triplicate ECGs remains \geq 470 ms, patient must not be dosed. Pre-dose ECG monitoring is mandatory on days 1 and 5 of cycle 1, and day 1 of cycles 2 through 4. Post dose ECG (3 hours (\pm 15 minutes) post dosing) is mandatory only on days 1 and 5 of cycle 1.

If a screening, pre-dose, or post-dose ECG shows a QTcF \geq 500 ms, patient is not eligible for further treatment. If any of these mandatory ECGs show QTcF \geq 470 msec or 60 msec above baseline, dosing should be held and the above specified measures including follow-up triplicate ECGs and correction of electrolyte abnormalities should be performed. If QTcF abnormality resolves, patients should resume treatment and have QTcF checked pre-dose on day 1 of each cycle for at least the next 3 subsequent cycles. Additional QTcF monitoring should be performed if clinically indicated. If a patient cannot be dosed due to prolonged QTcF for more than 7 days since last dose, patient must be discontinued from study treatment.

Table 7-3 Dose Reductions for QTc Prolongation

Time Point	Average QTcF*	Action
Screening and pre-dose cycle 1 day 1	\geq 470 msec	Delay treatment Correct any electrolyte abnormal values ** and repeat ECG, if the average QTcF \geq 470 msec, do not dose
	Above 500 msec	Patient is not eligible

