8.1 Visit schedule

Table 8-1 Evaluation and visit schedule

	Pre-HCT (Screening, not required)	Prior to maintenance (Enrollment: +45 to +180) [§]	Cycle #1 (start between +90 and +180)	Cycle #2****	Cycle #3****	Cycle #4****	Cycle #5****	Cycle #6****	Cycle #7****	Cycle #8****	Cycle #9****	Cycle #10*** *	Cycle #11*** *	Cycle #12*** *	End of study visit (4 weeks (± 14 days) follow up after the first dose of cycle #12)
Consent	X ⁺	X													
Enrollment		X													
H&P (SOC)		X	X ^{SS§}	X	X	X	X	X	X	X	X	X	X	X	X
Concomitant medications		X													
Toxicity (adverse event (AE)) assessment ^{SS}			X	X	X	X	X	X	X	X	X	X	X	X	X
Vital signs (SOC)		X ⁺⁺	X	X	X	X	X	X	X	X	X	X	X	X	X
EKG		X	X [*]	X ^{**}	X ^{**}	X ^{**}									
CBC and CMP (SOC)		X	X ^{***}	X ^{***}	X	X	X	X	X	X	X	X	X	X	X
PT/INR/PTT		X			X			X							X
LDH, cholesterol panel, GGT, uric acid		X													
Urinalysis		X													X
TSH, free T4		X													X
Serum pregnancy test ⁺⁺⁺		X	X	X	X	X	X	X	X	X	X	X	X	X	
SPEP, UPEP and serum free		X			X			X			X			X	

Confidential

light chains (SOC)															
Pneumococcal-13 conjugate vaccine (at around day +90 – SOC)		X [#]													
Peripheral blood research samples	X	X	X ^{****}	X	X			X			X				X
Bone marrow research samples	X [@]	X													X
Stem cell graft research samples	X														

*Single 12 lead EKG will be performed for pre-dose and 3 hours (± 15 minutes) post-dose on days 1 and 5 of cycle 1. A total of 4 EKGs during cycle 1 will be performed.
 **Single 12 lead EKG will be performed for pre-dose on day 1 of cycle 2 and beyond at each cycle (at least through cycle 4). If no significant QTcF prolongation is noted during the first cycle, then QTc monitoring is no longer required beyond cycle 4 (and may be performed at the investigator’s discretion). One EKG per cycle from cycle 2 to 4 (minimum).
 ***CBC to be performed weekly during cycle #1 and #2. CBC/CMP will also be performed on day 5 of cycle 1.
 ****Window to start cycles #2 to #12 would be ±7 days from the planned first day of each cycle.
 + Screening consent for research samples (bone marrow, peripheral blood and stem cell graft)
 ++ Height will be measured at screening visit prior to starting panobinostat maintenance therapy
 +++ Only for women of child bearing potential
 ++++ Peripheral blood research samples will be also collected on day 5 of cycle 1.

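### The ±7-day window for starting cycles 2 to 12 conflicts, on its early side, with the every-other-week, 28-day dosing rules

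*Combined protocol and SAP*

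**What the plan says.** The four-asterisk footnote to Table 8-1 reads: "Window to start cycles #2 to #12 would be ±7 days from the planned first day of each cycle". It sets no minimum interval since the last dose. It also does not say whether the planned first day follows the original calendar or the actual start of the previous cycle.

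The dosing rules are in other sections:

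- Section 7.1 gives Cohort B 10 mg "daily x 7 days, every other week, of a 28-day schedule (Cohort B". Cohort A takes 20 mg three times a week, also every other week in 28 days.
- Section 7.3: "The planned treatment is for a total of 12 cycles (48 weeks". Section 3 shows the same sum: "Maintenance therapy will be prescribed for a maximum for 12 cycles (4 weeks x 12 cycles = 48 weeks) for both cohorts".
- Section 7.4.1 makes the next cycle conditional: "If no grade 3 or 4 toxicities occur after completing a 28-day cycle of panobinostat maintenance therapy". Other toxicity outside the blood counts must also have settled to at most grade 1, and minimum blood counts must be met.

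The primary objective (Sections 4.1 and 13.1.3) is the tolerability and safety of these two schedules, reported as the 12-cycle completion rate and relative dose intensity (RDI) per cohort.

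**The concern.** Day 1 of a cycle is a dosing day: Section 8.3 has patients seen then, and Section 7.4.3 calls for a pre-dose ECG on day 1 of cycles 2 to 4. A window for starting cycles is therefore a window for giving drug. Taken literally, its early side puts the next day 1 on day 22, while Section 7.4.1 has a 28-day cycle completed first. One investigator could treat a day-22 start as compliant while another records a deviation.

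The off-week is what makes each schedule every-other-week. If it is shortened, the cohort has not received the schedule whose tolerability is being reported, and the planned outputs would not show it. Completion counts cycles. RDI in Section 13.1 is milligrams received over milligrams planned, with no time term. The dosing report covers doses missed, reduced or delayed, but not cycles started early.

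**Working it through.** **Inputs.** The doses and 28-day cycle come from Sections 7.1 and 7.3, and the window from Table 8-1. Dosing in weeks 1 and 3 is inferred from the every-other-week wording, day-1 dosing, and the reduced Cohort B level on days 1, 3, 5 and 7 (Table 7-1). Cohort A dosing days 1, 3, 5, 15, 17 and 19 are an assumption.

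**Plan's own figures.** 12 × 4 = 48 weeks. Dose per dosing week: A 3 × 20 = 60 mg, B 7 × 10 = 70 mg. All agree with Sections 3 and 7.3.

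**Early start by shift s (s ≤ 0).** The planned next day 1 is day 29; the earliest is 29 − 7 = day 22. Dose-free days before the next cycle are 7 + s in Cohort B and 9 + s in Cohort A.

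| Shift (days) | B: mg, days 15-28 | B: dose-free days | B: longest daily run | A: mg, days 15-28 | A: dose-free days |
|---|---|---|---|---|---|
| 0 | 7 × 10 = 70 | 7 | 7 | 3 × 20 = 60 | 9 |
| −3 | 10 × 10 = 100 | 4 | 7 | 5 × 20 = 100 | 6 |
| −6 | 13 × 10 = 130 | 1 | 7 | 6 × 20 = 120 | 3 |
| −7 | 14 × 10 = 140 | 0 | 14 | 6 × 20 = 120 | 2 |

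Every early start shortens the second off-week, but only −7 joins the two Cohort B dosing weeks into 14 daily doses.

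**Undefined anchor.** If planned days stay on the original calendar, a start L days late followed by one on its calendar date leaves 28 − L days between starts. L = 4 gives 24 days, with 24 − 21 = 3 dose-free days in Cohort B. L = 7 gives 21 days and none. The off-week can thus be lost without any early start. A start 7 days late followed by one 7 days early gives 28 − 14 = 14 days, so the new cycle would begin on day 15 of the unfinished one.

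**Comparison with the tabulated experience.** Tables 2-1, 2-3 and 2-4 contain only three-times-a-week regimens. Daily dosing is absent from them even for the planned 7 days. Cohort A started 7 days early every time would settle into two weeks on and one week off in 21 days at 20 mg three times a week. That is the panobinostat schedule of the phase 2 and phase 3 trials with bortezomib and dexamethasone in Table 2-4.

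**The case against.** The strongest reply is that the footnote belongs to a visit schedule, while dosing is governed by Section 7, so the footnote only gives scheduling slack. That may be the intent, but the wording is about starting cycles and no text ranks the two rules. Equally, a reader might infer that the protocol plainly authorises dropping the off-week. The documents do not support that either, because Section 7.4.1 points the other way. What stands is an unresolved conflict.

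A reader might also infer a demonstrated safety hazard, which is not shown. A new cycle requires the toxicity and count criteria of Section 7.4.1. Electrolytes must be at or above the lower limit of normal "before the patient is re-dosed with oral panobinostat" (Section 7.1.1). ECG checks apply too: "Pre-dose ECG monitoring is mandatory on days 1 and 5 of cycle 1, and day 1 of cycles 2 through 4". At −7 the two adjoining weeks carry 140/2 = 70 mg/week in B and 120/2 = 60 mg/week in A. Weekly three-times-a-week dosing gives 60 mg/week at 20 mg (309 patients in Table 2-3) and 120 mg/week at 40 mg (163 patients). Section 2.2.2 names 40 mg as the recommended phase 2 dose for the weekly schedule in myeloma, and Section 5 says the maintenance dose was set below MTD dosing. This largely answers the safety point for Cohort A. It does so less well for Cohort B, which would be dosed daily, and none of these data are described as post-transplant maintenance. The checks also do not restore an off-week. Mandatory ECGs can end after cycle 4, while the window runs to cycle 12.

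The data would not be lost: Sections 7.1, 7.4 and 7.6 require doses, changes and visit intervals to be recorded. Only a listing is missing.

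**Conclusion.** The conflict is real and worth correcting, as a cheap improvement. If the early side is used in full, Cohort B takes 14 consecutive daily doses and 140 mg instead of 70 mg in days 15-28, while Cohort A takes 120 mg instead of 60 mg. The main concern is Cohort B, together with whether both cohorts receive the schedules under test. The figures rest on dosing in weeks 1 and 3 and, for Cohort A, on the assumed dosing days.

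Two stronger conclusions should not be drawn. First, no bias in the completion rate is shown. Section 13.1 counts completion of 12 cycles whatever the dose modifications, and the documents give no indication of how often cycles would start early. Second, a reader could compute a compressed course of 11 × 21 + 28 = 259 days against 336, or 336/259 = 1.30 times the planned intensity. That needs all 11 starts to be 7 days early with the calendar reset each time. On a fixed calendar the course shortens by at most 7 days, to 329. The 1.30 is a theoretical bound and carries no weight here.

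**What to change.** Amend the footnote as follows, with cross-references in Sections 7.3 and 7.4.1:

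1. Define the planned first day of cycles 2 to 12 as day 29 counted from the actual first dose of the previous cycle, reset after any delay.
2. Allow the first dose 0 to +7 days from that day. Delays for toxicity follow Sections 7.4.2, 7.4.3 and 7.4.5 and are not window violations. Without the reset and this exception, a toxicity delay of more than 7 days on a fixed calendar would leave no compliant start date.
3. Keep ±7 days only for assessments that do not trigger dosing.
4. List any shortened off-weeks per cohort beside the missed, reduced and delayed doses, using data already recorded under Sections 7.4 and 7.6.

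Within this window cycles last 28 to 35 days, the second off-week in Cohort B lasts 7 to 14 days, and its longest daily run stays at 7.

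The cost is one footnote, two cross-references and one listing. No cycle could start early, so even a one-day-early start becomes a deviation. Late starts carry forward: if all 11 are 7 days late, the course is 11 × 35 + 28 = 413 days, or 59 weeks instead of 48. Delays are already permitted, both by the late side of the present window and under Section 7.4.5.

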 # It is advised that the standard of care heptavalent pneumococcal conjugate vaccine be administered at around day +90 prior to the initiation of maintenance therapy.
 @ Archived (formalin-fixed paraffin embedded) bone marrow clot will be accessed to identify myeloma index clones for high-throughput sequencing.
 § Patients can be enrolled after autologous HCT without having the pre-HCT screening visit (which is not require).
 §§ Only grade ≥ 3 adverse event (AE) will be collected.
 §§§ Patients will be evaluated (history and physical) on day 5 of cycle 1.

Abbreviations: SOC, standard of care

8.2 Efficacy assessments

All subjects will be evaluated every 3 months with multiple myeloma restaging (standard of care) including serum protein electrophoresis (SPEP), urine protein electrophoresis (UPEP) and serum free light chains. Response assessment will be performed approximately at cycle 3, 6, 9, and 12 of maintenance panobinostat therapy. Responses will be classified by according to the IMWG response criteria (Appendix C).

8.3 Safety assessments

Safety assessments will consist of monitoring and recording unexpected grades ≥ 3 adverse events and serious adverse events, the regular monitoring of hematology, blood chemistry and urine values, vital signs, ECOG performance status, and the regular physical examinations and ECG assessments. All patients will be seen on day 1 of each cycle throughout the maintenance therapy until disease progression or unacceptable toxicities occur (Table 8-1). Additional evaluations may be performed if clinically indicated.

Adverse events will be assessed according to the Common Toxicity Criteria for Adverse Events (CTCAE) version 4.03. CTCAE v4.0 can be accessed on the NIH/NCI website at (http://evs.nci.nih.gov/ftp1/CTCAE/CTCAE_4.03_2010-06-14_QuickReference_5x7.pdf)

8.3.1 Adverse events

Information about unexpected grades ≥ 3 adverse events, whether volunteered by the subject, discovered by investigator questioning, or detected through physical examination, laboratory test or other means, will be collected and recorded and followed as appropriate.

An adverse event is the appearance or worsening of any undesirable sign, symptom, or medical condition occurring after starting the study drug even if the event is not considered to be related to study drug. Medical conditions/diseases present before starting study drug are only considered adverse events if they worsen after starting study drug. Abnormal laboratory values or test results constitute adverse events only if they induce clinical signs or symptoms, are considered clinically significant, or require therapy.

The occurrence of adverse events should be sought by non-directive questioning of the patient at each visit during the study. Adverse events also may be detected when they are volunteered by the patient during or between visits or through physical examination, laboratory test, or other assessments. As far as possible, each adverse event should be evaluated to determine:

1. the severity grade (moderate, severe) or (grade 3-4) – only grades adverse events will be reported its relationship to the study drug(s) (suspected/not suspected)
2. its duration (start and end dates or if continuing at final exam)
3. action taken (no action taken; study drug dosage adjusted/temporarily interrupted; study drug permanently discontinued due to this adverse event; concomitant medication taken; non-drug therapy given; hospitalization/prolonged hospitalization)
4. whether it constitutes a serious adverse event (SAE)

All adverse events should be treated appropriately. Such treatment may include changes in study drug treatment including possible interruption or discontinuation, starting or stopping concomitant treatments, changes in the frequency or nature of assessments, hospitalization, or

any other medically required intervention. Once an adverse event is detected, it should be followed until its resolution, and assessment should be made at each visit (or more frequently, if necessary) of any changes in severity, the suspected relationship to the study drug, the interventions required to treat it, and the outcome.

Information about common side effects already known about the investigational drug can be found in the [\[Investigators' Brochure\]](#) or will be communicated between IB updates in the form of Investigator Notifications. This information will be included in the patient informed consent and should be discussed with the patient during the study as needed.

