4.1 Primary

To determine tolerability and safety profile of 2 different dosing schedule of single agent panobinostat maintenance therapy for a maximum of 12 intended cycles after autologous HCT in patients with multiple myeloma. We will calculate relative dose intensity (RDI) for each cohort.

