8.3.3 Physical examination

Physical examination will be performed which comprises examination of skin, lungs, heart, abdomen, lymph nodes, and extremities at minimum.

Significant findings made after the start of study drug which meet the definition of an grades ≥ 3 Adverse Event must be recorded.

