12.1 Data collection and monitoring

Investigators must enter the information required by the protocol onto Case Report Forms (CRFs) for unexpected grades ≥ 3 adverse events and serious adverse events. Additional data to be captured may be identified at the time of study activation or review by ongoing monitoring committees.

13 Statistical methods

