13.1 Statistical methods and data analysis

This is an open label study of 2 different panobinostat maintenance dosing schedules after autologous HCT in patients with multiple myeloma. There are 2 cohorts and patients will be enrolled sequentially to cohort A, then to cohort B. The sample size is 30 patients for this trial (15 for each cohort). We expect that at least 2/3 of each cohort will complete 12 cycles of maintenance panobinostat (regardless of dose modification) and will be evaluable for the primary endpoint. The widths of 95% confidence interval (CI) are 0.356, 0.438, 0.487, 0.514, and 0.522 when the proportions of patients tolerating 12 cycles of maintenance are 0.9, 0.8, 0.7, 0.6, and 0.5, respectively.

A patient who withdraws from the study due to reasons other than death, disease progression or toxicity will be replaced and is considered as non-evaluable for primary endpoint. The proportion of patients tolerating the therapy will be reported with 95% CI. All 30 patients are eligible for secondary endpoints. We will compute the overall response rates before the transplant, after autologous HCT, and after the completion of maintenance therapy, and at best response. The OS and PFS will be estimated using the Kaplan-Meier method. We will also report the incidences of all grades and grade ≥ 3 toxicities. The two-sided 95% CIs for

proportion, and OS and PFS will be computed using the Clopper-Pearson method and the Greenwood formula, respectively. In addition, the frequency of B cell precursor as well as other cell subsets, and their 95% CI will be evaluated using t-distribution. If data do not meet normality assumption, the power transformation (e.g., log-transformation) will be conducted. Those patients who are not in CR before the transplant would be most suitable for T-effector activity analysis. This will be examined by the paired t-test or the Wilcoxon signed-rank test, depending on the data distribution.

Relative dose intensity (RDI) represents the ratio of the amount of a drug actually delivered [actual dose intensity (DI)] to the amount planned (planned DI). The purpose of calculating RDI is to evaluate whether the planned DI of a chemotherapy treatment was actually achieved which may suggest the feasibility of planned treatment regimen. There are multitude of reports demonstrating a correlation between RDI and survival in cancer treatment.

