13.1.5 Early stopping rule

No early stopping rule is considered in this study but the safety and efficacy data will be continuously monitored by PI and the supporting company (Novartis). Patient accrual will be temporarily suspended if the completion rate of maintenance therapy at the end of 12 cycles is equal to or less than 60% or if the non-hematologic grade 3 or 4 toxicity rate is 40% or higher. The PI and the supporting company (Novartis) will review safety data, and the study may be early terminated based on the review results.

14 Procedures and instructions

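### Three sections record only unexpected grade ≥3 adverse events, two other places record all grade ≥3 events, and neither rule can supply the all-grade incidence of symptoms that section 13.1 promises

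*Combined protocol and SAP*

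**What the plan says.** The combined protocol and SAP states the adverse event (AE) recording rule in several places, in two forms.

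- With the *unexpected* filter: section 8.3 ("Safety assessments will consist of monitoring and recording unexpected grades ≥ 3 adverse events and serious adverse events"), section 8.3.1 ("Information about unexpected grades ≥ 3 adverse events, whether volunteered by the subject") and section 12.1, which has investigators enter data "onto Case Report Forms (CRFs) for unexpected grades ≥ 3 adverse events and serious adverse events".
- Without the filter: the Table 8-1 footnote in section 8.1 ("Only grade ≥ 3 adverse event (AE) will be collected") and section 8.3.3 ("Significant findings made after the start of study drug which meet the definition of an grades ≥ 3 Adverse Event must be recorded").

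Item 1 of the list in section 8.3.1 should give the reporting threshold, but the grade has dropped out of the sentence and the item settles nothing.

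The analysis section asks for more than either form: "We will also report the incidences of all grades and grade ≥ 3 toxicities" (section 13.1). Section 13.1.5 suspends accrual if 12-cycle completion is too low "or if the non-hematologic grade 3 or 4 toxicity rate is 40% or higher". It names no data source for that rate.

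The primary objective in section 4.1 is "To determine tolerability and safety profile of 2 different dosing schedule of single agent panobinostat maintenance therapy".

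**The concern.** The safety profile is half of the primary objective, and the AE records are its main source for symptoms. Staff working from section 12.1 and staff working from the Table 8-1 footnote could build different AE datasets. Section 13.1 then asks for an all-grade table that neither dataset can fill for symptomatic events.

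Section 2.1.3 describes gastrointestinal events, mostly grade 1/2, as the most common AEs of this drug. For up to a year of maintenance, low-grade symptoms are a large part of what tolerability means. If they are not recorded at the visit, they are hard to reconstruct afterward. There is a second risk: grade ≥3 events of types already known for the drug could be left off the AE form because they are not unexpected.

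**Working it through.** **Design figure.** The only design figure is the set of 95% CI widths in section 13.1 for completion proportions 0.9, 0.8, 0.7, 0.6 and 0.5. Clopper-Pearson with n = 15 gives 0.3561, 0.4376, 0.4868, 0.5138 and 0.5224. The plan states 0.356, 0.438, 0.487, 0.514 and 0.522. They agree, and no AE record enters them.

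**Step 1: what each rule captures.** *Unexpected* is not defined for AE collection. The nearest sense is in section 10.1.2, where an SAE not yet documented in the Investigator's Brochure or package insert is treated as new.

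| Event | 8.3, 8.3.1, 12.1 | Table 8-1 footnote, 8.3.3 |
|---|---|---|
| SAE | recorded (8.3, 12.1) | reported under 10.1.2 |
| Non-serious grade ≥3, new type | recorded | recorded |
| Non-serious grade ≥3, known type | not recorded, if the 10.1.2 sense applies | recorded |
| Non-serious symptomatic grade 1-2 | not recorded | not recorded |
| Laboratory toxicity, any grade | gradable from scheduled results | gradable from scheduled results |

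Row 4 conflicts with the all-grade promise under both rules. Row 3 affects the grade ≥3 promise under one rule only.

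**Step 2: scale, for one symptom.** Inputs are Table 2-1 and the text of section 2.1.3, every-other-week schedule.

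- Any-grade fatigue: (18 + 12 + 15)/(28 + 18 + 24) = 45/70 = 64.3%, which reproduces the plan's figure.
- Grade 3/4 fatigue: 15.7%, with no denominator given. It fits 11/70, but 13/83 and 14/89 also round to 15.7%.
- If both refer to the same patients, worst grade 1-2 is 64.3 − 15.7 = 48.6 points, and 48.6/64.3 = 75.6% of patients with fatigue.
- Applied to 30 patients: 30 × 0.643 = 19.3 with fatigue, 30 × 0.486 = 14.6 with grade 1-2 only, and 30 × 0.157 = 4.7 with grade 3/4.

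Those patients took 30 to 60 mg and came from other studies; the doses here are 20 mg and 10 mg. This shows scale and is not a forecast.

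**Step 3: the 40% trigger, only if it is read from the filtered records.** The trigger needs 0.40 × 15 = 6 patients of 15, or 0.40 × 30 = 12 of 30. Let p be the true patient-level rate and f the share of affected patients whose event is recorded. The chance of reaching the trigger is P(X ≥ r), with X binomial(n, p × f). Both p and f are assumptions.

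| p | n | f = 1 | f = 0.75 | f = 0.5 |
|---|---|---|---|---|
| 0.40 | 15 | 0.597 | 0.278 | 0.061 |
| 0.40 | 30 | 0.569 | 0.159 | about 0.01 |
| 0.50 | 15 | 0.849 | 0.517 | 0.148 |
| 0.50 | 30 | 0.900 | 0.456 | 0.051 |

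The direction is clear. The values are full-enrollment illustrations, not operating characteristics of the plan.

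**The case against.** The strongest reply is that section 12.1 is not a closed list. Its next sentence lets further data be identified at study activation or by monitoring committees, and the case report form itself is not in the documents. Section 12.1 also names no dosing, response or laboratory data, which the trial plainly needs. This stands as a limit on what section 12.1 proves alone. It does not remove the conflict: an open option is not a rule for grade 1-2 events, and the Table 8-1 footnote excludes them in terms.

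Second, many of the events leave a trace elsewhere. Section 8.3.1 has AEs sought at every visit. Table 7-2 interrupts dosing for grade 3-4 fatigue and for several grades of diarrhea, nausea and vomiting. Section 7.4 records every interruption or change, section 7.4.4 records reasons for discontinuation, and section 13.1 reports missed, reduced and delayed doses by cohort. This is partial mitigation. A dosing record is not a graded event, and controlled grade 1-2 nausea or vomiting changes no dose.

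Third, data go into one institution's database with routine internal monitoring, and section 13 plans no formal comparison of toxicity between cohorts. Both points lower the stakes; neither supplies the missing data.

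A reader might go further and infer that the grade ≥3 table will be incomplete. The documents do not support that without conditions, because the Table 8-1 footnote, if followed, captures those events. A reader might also add 15.7% fatigue to the 10.5% grade 3/4 gastrointestinal rate in Table 2-4 and call 26.2% the background for the trigger. That sum mixes an every-other-week schedule with a weekly-dosing trial in relapsed/refractory disease, covers two event classes and ignores overlap, so it is not a total non-hematologic rate.

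**Conclusion.** The concern holds in two parts of different strength.

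- **All grades:** under the rules as written, the incidence promised in section 13.1 cannot be produced for non-serious symptomatic events, whichever rule is followed. Laboratory toxicities are the exception.
- **Grade ≥3:** the documents conflict. Incidence is biased low if the filtered rule is followed and the word means absent from the Investigator's Brochure. It is complete if the Table 8-1 rule is followed.

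The size of either gap in this trial cannot be derived. The fatigue background, in which about three quarters of affected patients had worst grade 1-2, rests on 15.7% and 64.3% sharing a denominator.

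A reader might infer that the suspension trigger is already weakened. That follows only if the trigger is computed from the filtered AE records, and section 13.1.5 does not say so. Nor is the quantified primary analysis at risk: 12-cycle completion and relative dose intensity do not depend on AE forms, and SAE reporting has its own rule in section 10.1.2.

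**What to change.** 1. Use one recording rule in sections 8.3, 8.3.1, 8.3.3, 12.1 and the Table 8-1 footnote. Delete *unexpected*, so that every grade ≥3 AE and every SAE is recorded, with relationship to study drug noted as section 8.3.1 already asks. Repair item 1 of the section 8.3.1 list at the same time.
2. In section 13.1, choose one of three options: collect grade 1-2 AEs at the existing per-cycle toxicity assessments and amend the footnote; restrict the all-grade incidence to CTCAE-graded laboratory results; or remove it. With the second option, state that grading uses the results themselves, because section 8.3.1 counts an abnormal value as an AE only if it causes signs or symptoms, is clinically significant or needs therapy.
3. In section 13.1.5, name the complete grade ≥3 AE records as the data source for the 40% rate. Keep the existing definition of non-hematologic grade 3 or 4 toxicity, so that the trigger itself does not change.

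The cost is wording in about seven places, a few form fields, and modest extra data entry for 30 patients at visits that already include a toxicity assessment. It is least if the all-grade incidence is limited to laboratory results or dropped.
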